18.3. Study Procedures and Assessments

Patients will sign informed consent on OL Day 1 (their next regular scheduled visit following approval and activation of this amendment at the study site). All patients must have their OL Day 1 visit within 16 weeks after the approval and activation of this protocol at the study site. The enrollment period will end after this time. For detailed procedures see the Schedule of Activities ([Table 16](#)).

Study participants must be reminded to promptly notify site staff about any change in their health status. In addition to the protocol-specified visits, participants should attend clinic visits whenever clinically indicated or needed.

During the OL Period, study assessments will include monitoring as clinically indicated for adverse events, clinical laboratory tests, brief physical examinations including vital signs and drug accountability. For patients whose cancer has not progressed radiographically, scans (CT/MRI and bone scan) will be performed every 6 months until the patient’s cancer progresses radiographically by local determination.

The following laboratory values are recommended to be evaluated throughout the study in accordance with the schedule of activities (SOA). These evaluations are to take place locally, per each Institution’s SOC:

- Hematology: hematocrit, hemoglobin, platelet count, red blood cell count, white blood cell count with differential, and absolute neutrophil count must be obtained, or be able to be calculated.

- Comprehensive chemistry panel: albumin, alkaline phosphatase, ALT, AST, creatinine, blood urea nitrogen (BUN), Ca⁺⁺, total CO₂ (bicarbonate), glucose, Na⁺, K⁺, Cl⁻, total bilirubin, and testosterone.
- PSA.

Patients in survival follow-up will be followed for their survival status, new anti-prostate cancer therapies and scans every 6 months until they progress on the first anti-prostate cancer follow-up therapy.

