8.5.5.2. Clarification in Reporting of Deaths

As overall survival is one of the study endpoints, all patients must be followed for survival status until death, and information relating to the death (eg, date and primary cause) should be obtained and recorded. Deaths due to prostate cancer should be recorded as such by the investigator to allow for determination of prostate cancer-specific survival.

Fatal events (regardless of relationship to study drug) should be reported as serious adverse events during the treatment-emergent safety reporting period (through 30 days after permanent treatment discontinuation).

Death is not an adverse event but is an outcome of an adverse event. For this protocol, reports of death without an adverse event will be managed as expedited reports (SUSARs) until the sponsor receives additional information.

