18.1. Rationale and Treatment Plan

Primary endpoint analyses demonstrated that the primary efficacy endpoint of metastasis free survival (MFS) was established and the safety profile of enzalutamide was confirmed, therefore, the treatment codes for all patients will be unblinded and an open-label treatment period is being implemented. The final analysis of the key secondary endpoint for overall survival (OS) will be performed as planned. Patients will continue to receive their originally assigned study treatment in this open-label (OL) study period. Patients assigned to the placebo plus leuprolide arm will no longer take the placebo capsules. No crossover treatment will be implemented.

For patients whose cancer has not progressed radiographically, locally (change was effective as of 31-Mar-2023) performed scans (CT/MRI and bone scan) will be conducted until the patient's cancer progresses radiographically. Scans read centrally by blinded independent central reviewer (BICR) ceased as of 31-Mar-2023. Prostate-specific antigen (PSA) levels will also be done at a local lab and monitored by the investigator per standard of care (SOC) effective date of 31-May-2023. Patients who are in treatment suspension (due to prior undetectable PSA at study Week 36) will continue to have their PSA values, done at the local lab, evaluated by the investigator every 3 months for possible treatment reinitiation per protocol criteria. For details, refer to [Table 16](#).

Patients who discontinue study treatment or withdraw consent for further treatment will continue safety follow-up and long-term follow-up assessments per protocol (see [Section 18.8](#)). Long-term follow-up data including survival status, documentation of new antineoplastic therapies for prostate cancer, skeletal-related events, and progression on first subsequent therapy (PFS2) will be collected every 12 weeks until the final OS analysis. The associated endpoints will be summarized descriptively at the time of the final OS analysis.

Patients who receive any treatment other than their assigned study treatment for prostate cancer after unblinding will not be eligible for this OL period. All patients who permanently discontinue study drug treatment will remain in the study, complete safety follow-up, and subsequently commence long-term follow-up.

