16. Performed, collected and assessed locally per Institution’s SOC. Hematology and serum chemistry. Report any clinically significant abnormalities as adverse events per CTCAE v4 criteria. PSA levels for patients in treatment suspension should be entered into the study database.
17. If missed during regularly scheduled visit.
18. Perform and assess PSA locally. Evaluate if PSA value meets threshold for treatment reinitiation in patients on treatment suspension, if so study drug dispensing should be arranged. The investigator to monitor PSA values for PSA progression. Refer to Section [18.3.4](#).
19. May obtain at clinic visits, by telephone contact, chart review, etc. Includes survival status, new antineoplastic therapies for prostate cancer, skeletal-related events, and PFS2 up to final OS analysis.

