18.8. Safety Follow-up and Long-Term Follow-Up

Patients are to have a safety follow-up approximately 30 days after the last dose of OL study treatment. If a new antineoplastic or investigational anticancer treatment is initiated before 30 days after the last dose, then safety follow-up should occur immediately before starting any new treatment (Table 17).

Table 17. Safety Follow-Up Procedures (Open-Label Period)

Activity/Assessment	Comment
General Activities	
Vital signs and physical examination	As clinically indicated, measure blood pressure, heart rate, temperature and weight. Assess body systems per institution's SOC at the study site and as clinically indicated by symptoms.
ECOG performance status	Refer to Table 13.
Symptomatic skeletal events	Record use of radiation therapy (external beam radiation therapy or radionuclides) or surgery to bone for prostate cancer, findings of clinically apparent pathologic bone fracture or of spinal cord compression, and use of opiate and/or systemic antineoplastic therapy due to bone pain.
Adverse events review	Record any new or ongoing adverse events.
Concomitant medications review/contraceptive check	Record any new medications for prostate cancer, hormonal, antineoplastic therapies, and opiates.
Study drug accountability (if applicable)	Record study drug returned and remind patient to return all study drug.
Local Laboratory Evaluations	
Serum chemistry, hematology	Performed per SOC, refer to analytes listed in Section 18.3

Long-term follow-up data will be collected every 12 weeks. The information collected will include survival status, new antineoplastic therapies for prostate cancer, skeletal-related events, and PFS2 (Table 18).

Table 18. Long-Term Follow-Up Procedures (Open-Label Period)

Activity/Assessment/Timing	Comment
General Activities	
Symptomatic skeletal events	Record use of radiation therapy (external beam radiation therapy or radionuclides) or surgery to bone for prostate cancer, findings of clinically apparent pathologic bone fracture or of spinal cord compression, and use of opiate and/or systemic antineoplastic therapy due to bone pain.

Table 18. Long-Term Follow-Up Procedures (Open-Label Period)

Activity/Assessment/Timing	Comment
Other information	Survival status. Subsequent therapies for prostate cancer, including opiate medication to treat bone pain. Dates of investigator assessed progression on first subsequent therapy, including clinical, radiographic or PSA progression.

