Radiographic assessments → Perform at 24-week intervals (± 14 days)	Includes abdominopelvic CT/MRI and whole-body radionuclide bone scan for patients who have not yet had radiographic progression.

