6.2.4. Overall Survival

OS is defined as the time in months between randomization and death due to any cause. One interim analysis and a final analysis of overall survival will be performed. The first interim will be performed at the time of the final analysis of the MFS primary endpoint. The overall survival will be compared between treatment groups using a 2-sided stratified log rank test. Patients without an event date will be censored at the date of the last contact.

At the time of final analysis of OS, subgroup analyses will be conducted using the same analysis methods as for the subgroup analyses of MFS described in Section 6.6.

At the final analysis of OS, an additional confounding factor for the OS analysis may come from patients who choose to access commercial enzalutamide, combination of enzalutamide and leuprolide and other commercially available treatments for the patients. The sponsors may explore the effect of crossover and post-study systemic anticancer therapy using rankpreserving structural failure time model (RPSFTM), and the inverse probability of censoring weighting (IPCW) method if appropriate. Justifications, limitations and assumptions of RPSFTM (Robins & Tsiatis 1991) and IPCW (Robins & Finkelstein, 2000) methods will be adequately evaluated.

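### Protocol 18.3 can be read as ending survival follow-up at progression on the first follow-up therapy, against the rest of the plan; read as a scan rule only, it still conflicts with Table 18

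*Protocol*

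**What the plan says.** Protocol 18.3 closes by stating that patients in survival follow-up are followed for "survival status, new anti-prostate cancer therapies and scans every 6 months until they progress on the first anti-prostate cancer follow-up therapy". Three items share one verb. One interval and one stopping point end the list.

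Other current text sets a different rule for survival status and new therapies:

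- **Protocol 18.1:** long-term follow-up data, with survival status first in the list, "will be collected every 12 weeks until the final OS analysis".
- **Protocol Table 16:** the long-term follow-up column is every 12 weeks. Note 19 gives the content and end point: "Includes survival status, new antineoplastic therapies for prostate cancer, skeletal-related events, and PFS2 up to final OS analysis".
- **Protocol 18.8:** "Long-term follow-up data will be collected every 12 weeks. The information collected will include survival status, new antineoplastic therapies for prostate cancer". This section gives the interval but no end point.
- **Protocol 8.5.5.2:** "all patients must be followed for survival status until death".
- **SAP 5.1.2:** every 12 weeks until the final OS analysis.

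On scans, Table 18 (in 18.8) reads "Includes abdominopelvic CT/MRI and whole-body radionuclide bone scan for patients who have not yet had radiographic progression", at 24-week intervals. Table 16 note 8 likewise ends scans at locally confirmed radiographic progression.

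For the OS analysis, SAP 6.2.4 states: "Patients without an event date will be censored at the date of the last contact". Protocol 18.9 and SAP 5.1.2 leave OS as the only efficacy endpoint still to be formally tested.

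**The concern.** A site that takes the 18.3 sentence at face value would contact a patient for survival every 6 months and stop once he progresses on his first follow-up therapy. His later death might then never reach the database, and SAP 6.2.4 would censor him at his last contact.

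Two things would be at stake.

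- **Informative censoring.** Contact would end at a clinical event after which the risk of death is probably higher. If treatment changes the time to that event, the censoring also differs by arm. Waiting for more deaths does not remove this bias.
- **Event count.** Final OS is triggered at 271 deaths in three arms (Protocol 10.7 and 18.9). Unrecorded deaths postpone the trigger, or cost power if the analysis is run on a calendar date anyway.

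The scan part of the sentence is a separate conflict. A patient with radiographic progression before his next therapy would keep being scanned under 18.3 but not under Table 18. A patient who progresses by PSA on that therapy, with no radiographic progression, would stop under 18.3 but continue under Table 18.

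**Working it through.** **1. Two ways to read the sentence**

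| Reading of the closing phrase in 18.3 | Survival status and new therapies | Scans |
|---|---|---|
| Governs all three items | Conflicts with 18.1, Table 16 and note 19, 8.5.5.2 and SAP 5.1.2 on interval, end point or both; conflicts with 18.8 on interval | Conflicts with Table 18 and Table 16 note 8 on end point |
| Governs scans only | No conflict | Same conflict |

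Neither reading leaves the protocol consistent.

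**2. Reproduce the planned OS power**

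Inputs (Protocol 10.7 and 10.8): 191 deaths in the two blinded arms, hazard ratio 0.67, 1:1 within the comparison, two-sided alpha 0.05. With the Schoenfeld approximation and d deaths:

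power = Φ( √(d/4) × |ln 0.67| − z), with |ln 0.67| = 0.4005 and z = 1.96.

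For d = 191: √47.75 = 6.910; 6.910 × 0.4005 = 2.767; 2.767 − 1.96 = 0.807; Φ = 79.0%. The plan states 79.0%. At alpha 0.03 and 0.02 the formula gives 72.5% and 67.0%, against 72.3% and 67.0% stated. The planned figures reproduce.

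**3. Deaths that the sentence could affect**

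Section 18 was introduced after the primary metastasis-free survival analysis (Protocol 3.1 and 18.1), which is also the OS interim. Table 15 expects 82 blinded-arm deaths by then (82/191 = 43%). That leaves 191 − 82 = 109 exposed. This is an upper limit, because deaths between the interim cut-off and a site's activation of the amendment are not exposed either.

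**4. Effect of missing a share f of those deaths**

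The documents give no value for f, so the range is assumed. With the calendar cut-off not extended, d = 82 + 109 × (1 − f). If the cut-off instead waits for events, 109/(1 − f) true post-interim deaths are needed for 109 to be recorded.

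| f (assumed) | Deaths recorded, fixed cut-off | Power | True post-interim deaths needed to record 109 |
|---|---|---|---|
| 0 | 191 | 79.0% | 109 |
| 10% | 180.1 | 76.6% | 121 |
| 20% | 169.2 | 74.0% | 136 |
| 30% | 158.3 | 71.2% | 156 |
| 50% | 136.5 | 64.8% | 218 |
| 100% | 82 | 44.2% | not reached |

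**5. Direction of the bias**

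A simulation with wholly assumed inputs shows the mechanism. Control progression on next therapy was 25% at 5 years, with hazard ratio 0.6 for that event. Death without such progression was 5% to 15% at 5 years in both arms, median time from progression to death was 30 months, and the cut was at 96 months. Stopping contact at progression moved the OS hazard ratio from 0.70–0.81 to about 0.99–1.00. Treatment acted only through progression, and contact stopped from randomisation onward, which a rule introduced after the interim cannot do. The result gives a direction under these assumptions and no size for this trial.

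**The case against.** The strongest reply is that the closing phrase belongs to scans alone. Six months is the scan interval earlier in 18.3 and in 18.3.3, and nowhere else in the plan is it a survival interval. Section 18.3 itself sends the reader to Table 16 for detailed procedures, and Table 16 has the 12-week, to-final-OS rule. Protocol 9.1.3.4 monitors survival after discontinuation for any reason and allows survival sweeps. Harm needs a site to prefer one sentence over all of this, and nothing in the documents shows that any site did.

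Much of this stands. It makes the OS risk conditional and shows that the intended rule can be recovered. It does not settle the text, because the sentence does not limit its ending to scans, the sweep is optional, and the scans-only reading still contradicts Table 18 and Table 16 note 8.

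A second reply also stands in part: Table 18 leaves patients without protocol scans on the next therapy, but that matters little for progression-free survival on first subsequent therapy (PFS2). PFS2 is exploratory and investigator-determined from PSA, imaging or clinical progression, and is only summarised descriptively at final OS.

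A reader might infer that all 191 deaths are at risk, so that a 60% loss would leave about 76 and power near 42%. The plan's own figures rule this out: 76 is below the 82 deaths expected before Section 18 existed.

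**Conclusion.** The point holds as an inconsistency in operative text that needs correcting on either reading. On the literal reading it reaches the one endpoint still to be formally tested.

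The consequence for OS is conditional on sites following 18.3 literally. Because the final analysis is event-driven, the first effect of missed deaths is delay. Power falls only if the cut-off is not extended, to 76.6%–64.8% for an assumed 10%–50% loss of post-interim deaths, with 44.2% as the floor if all were missed. Informative censoring would remain in either case, and its size cannot be derived from the documents.

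Three assumptions carry this: the expected 82 interim deaths stand in for the actual count, the loss share is assumed, and the risk of death is taken to rise after progression on next therapy. The last is plausible, but the documents do not quantify it.

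A reader might go further and conclude that the protocol ends survival follow-up early, or that the OS result is already compromised. The documents support neither: several other provisions require survival follow-up to the final OS analysis or to death, and there is no evidence of what sites did.

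**What to change.** Split the last sentence of Protocol 18.3 in two.

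- **Survival status and new prostate-cancer therapies:** collected every 12 weeks until the final OS analysis for every patient, regardless of progression on any therapy, as 18.1, Table 16 and SAP 5.1.2 already require. Add the same end point to 18.8, which lacks one.
- **Scans:** state the rule separately and reconcile 18.3 with Table 18 and Table 16 note 8. Which scan rule applies is for the sponsor to decide.

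Tell sites by letter. Before the final OS cut-off, run the survival sweep that Protocol 9.1.3.4 permits, to recover any patient whose survival contact stopped early.

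The cost is a short text change, one letter and one sweep. The survival part adds no visits, because 12-weekly contact to the final OS analysis is already required elsewhere.

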18.3.1. Telehealth Visits

Telehealth visits may be used to assess participant safety and collect data points. Telehealth includes the exchange of healthcare information and services via telecommunication technologies (eg, audio, video, videoconferencing software) remotely, allowing the participant and the investigator to communicate on aspects of clinical care, including medical advice, reminders, education, and safety monitoring. The following assessments must be performed during a telehealth visit:

- Review and record study intervention(s), including compliance and missed doses.
- Review and record any AEs and SAEs since the last contact (see [Section 8](#)).
- Review and record any new concomitant medications or changes in concomitant medications since the last contact per [Section 18.6](#).
- Review for presence of symptomatic skeletal events.
- Review and record contraceptive method. Confirm that the participant is adhering to the contraception method(s) required in the protocol (see [Section 8.2.3](#)).

18.3.2. Safety Assessments

Safety data will continue to be collected in the OL period through 30 days after the last dose (ie, permanent discontinuation) of study drug including the period following protocol-specified treatment suspension (due to prior undetectable PSA at study Week 36) and resumption of study drug treatment through permanent treatment discontinuation per Protocol [Section 8](#). Assessments of safety will include all adverse events, clinical laboratory tests (hematology, serum chemistry), physical examinations and vital signs according to the Schedule of Activities for the OL treatment period ([Table 16](#)). Local clinical laboratory test results will no longer be required to be entered into the clinical database with the exception of the PSA levels collected for patients who are in treatment suspension. All second primary malignancies (with the exception of uncomplicated nonmelanoma skin cancers) must be reported as a serious adverse event (see [Section 8](#)).

18.3.3. Radiographic Assessments

For patients entering the OL treatment period whose cancer has not progressed radiographically, scans (CT/MRI and bone scan) will be performed locally every 6 months according to the Schedule of Activities (Table 16) until progression is identified radiographically. The study Investigator will review and assess the radiographic scans for disease progression. Study treatment will be stopped upon disease progression as assessed by the investigator. Patients who do not participate in the OL treatment period or withdraw consent for further treatment will continue long-term follow-up assessments per protocol (Table 18).

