	
monitored by the investigator per standard of care. Patients who are in treatment suspension will have their assigned treatment reinitiated if subsequent local laboratory PSA values increase to ≥ 2.0 ng/mL for patients with prior prostatectomy or ≥ 5.0 ng/mL for patients who had prior radiation therapy. Patients will not continue in the open-label period if they have had radiographic cancer progression.
 
Patients who do not participate in the open-label period or withdraw consent for further treatment will continue safety follow-up (within approximately 30 days after last dose) and long-term follow-up assessments per protocol. Long-term follow-up data (including survival status, new antineoplastic therapies for prostate cancer, skeletal-related events, and PFS2) will be collected every 12 weeks.
 
Day 1 of the open-label period will occur after consent is signed and eligibility is verified. No crossover treatment will be implemented. Sites must have all open-label Day 1 visits completed within 16 weeks after Institutional Review Board (IRB)/Ethics Committee (EC) approval of this protocol amendment. Patients who will receive any other treatment for prostate cancer after unblinding will not be eligible for the open-label enzalutamide period (these patients will remain in the study, complete safety follow-up, and subsequently commence long-term follow-up).
 
The complete details for the conduct of the open-label period are provided in Supplement 1: Open-Label Study Period.

DOUBLE-BLIND PERIOD	
The double-blind period has concluded and the open-label period is ongoing. The completed double-blind protocol has not changed.

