5.3. Permanent Treatment Discontinuation

Permanent treatment discontinuation is defined as cessation of randomized study drug treatment administration. Safety follow-up will be performed per [Section 5.4](#). Information on study discontinuation related to COVID-19 is provided in [Appendix 6](#).

Temporary treatment interruption (eg, due to an adverse event) is not considered permanent discontinuation.

Suspension of study drug treatment due to undetectable PSA is discussed in [Section 5.2.6](#).

The primary reasons that require patients to *permanently discontinue* randomized study drug treatment are as follows:

- Adverse event or intercurrent illness: Any intolerable adverse event that cannot be ameliorated by the use of adequate medical intervention or that in the opinion of the investigator or medical monitor would lead to undue risk if study treatment were continued. Refer to [Section 8](#).
- Gross noncompliance with protocol: The medical monitor or investigator and/or study management may request permanent treatment discontinuation in the event of a major protocol deviation, lack of cooperation, or noncompliance.
- Development of radiographic progression confirmed by central review after initial local read.
- Administration of prohibited concomitant therapy: Refer to [Section 7.2](#).
NOTE: Patients who discontinue due to administration of a prohibited concomitant therapy will remain in the study and complete safety follow-up assessments per [Section 5.4](#), then begin long-term follow-up per [Section 5.5](#).
- Laboratory abnormality defined by protocol as follows:

Creatinine >354 µmol/L (>4.0 mg/dL);

AST, ALT, or TBili >5 times the upper limit of normal;

Absolute neutrophil count ≤750/µL.
- Platelet count <50,000/µL.
- Seizure: Regardless of resolution of any identified etiology. Refer to [Section 8.5.5.1](#).
- Death: Refer to [Section 8.5.5.2](#).
- Loss to follow-up: Refer to [Section 5.6](#).
- Investigator conclusion that it is in the patient's best interest to discontinue therapy (eg, poor compliance with either protocol monitoring or with taking the study medications, etc.).
- Sponsor discontinuation of study: The sponsor reserves the right to terminate the study anytime as described in [Section 13.6](#). The sponsor will terminate this study following completion of the study objectives, or earlier if deemed necessary.

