18.3.4. Monitoring PSA Progression

PSA levels will be measured and monitored by the investigator locally to make decisions during the OL study period. For details, refer to Schedule of Activities (Table 16).

Time to PSA progression is defined in Section 10.4.2.1.

For patients who have been in treatment suspension since Week 37 for undetectable (<0.2 ng/ml) PSA values at Week 36, the study investigator will directly monitor and assess the patient's locally obtained PSA levels. Open-labeled treatment will be reinitiated if subsequent local laboratory PSA values increase to ≥ 2.0 ng/mL for patients with prior prostatectomy, or ≥ 5.0 ng/mL for patients who had prior radiation therapy. If laboratory PSA values meet the requirement for treatment reinitiation, the patient should return to the study site as soon as possible for drug dispensing and reinitiation of study treatment.

Treatment reinitiation must be registered in the IWRS to obtain the enzalutamide treatment for patients on the enzalutamide treatment arms and provision of a 12 week supply of study drug for resumption of treatment. (Refer to the IWRS Site Manual). If a patient is on the leuprolide arm, they will restart leuprolide and continue with their subsequent IP administration (including leuprolide as applicable) at their next study visit. Study drug administration should continue regardless of PSA values until radiographic progression is confirmed by local imaging (CT/MRI) per investigator's assessment and the investigator considers continuing study drug not to be beneficial.

A prostate cancer nomogram will be provided to investigational sites for uniform calculation of the PSA doubling time.^[25]

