18.5. Duration of Treatment and Dose Modification

Open-label study treatment administration may continue for patients whose prostate cancer has not progressed radiographically.

Enzalutamide dose modification: patients who experience a grade 3 or higher toxicity that cannot be ameliorated by the use of adequate medical intervention may interrupt treatment for 1 week or until the toxicity grade improves to grade 2 or lower severity. Subsequently, study drug dosing may be restarted at the original dose (4 capsules/day [160 mg/day]) or a reduced dose (3 or 2 capsules/day [120 or 80 mg/day]) in consultation with the medical monitor.

There are no provisions for dose modification of leuprolide on this study. If enzalutamide is coadministered with a strong CYP2C8 inhibitor (eg, gemfibrozil), the dose of enzalutamide should be reduced to 80 mg once daily. If coadministration of the strong CYP2C8 inhibitor is discontinued, the enzalutamide dose should return to the dose used prior to initiation of the strong CYP2C8 inhibitor.

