18.7. Treatment Interruption and Discontinuation

Patients whose treatment is interrupted due to an adverse event and restarted will continue to have regularly scheduled study visits based on their enrollment date in the OL period.

Permanent treatment discontinuation is defined as cessation of randomized study drug treatment administration. *Temporary* treatment interruption (eg, due to an adverse event) is not considered permanent discontinuation. For more details, refer to [Section 5.3](#). Safety follow-up will be performed per [Table 17](#). Information on study discontinuation related to COVID-19 is provided in [Appendix 6](#).

Sponsor discontinuation of study: The sponsor has the right to terminate the study anytime. However, the sponsor will ensure that study treatment will be available to all patients who participate in the OL period for as long as they are deriving clinical benefit.

Patients who discontinue study treatment (with exception of patients who withdraw consent) will have safety follow-up approximately 30 days after the last dose or before initiating treatment with a cytotoxic chemotherapy or investigational agent for prostate cancer. If a new cytotoxic or investigational anti-cancer treatment is initiated before 30 days after the last dose of enzalutamide/leuprolide, then safety follow-up should occur immediately before starting the new treatment. Long-term follow-up will commence after completion of safety follow-up. For more details, refer to [Section 18.8](#).

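### The open-label supplement gives conflicting instructions on stopping study drug for a patient who has progressed radiographically but is still judged to benefit

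*Protocol*

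**What the plan says.** Four places in the protocol address stopping at radiographic progression in the open-label period.

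- **Section 18.3.3 (Radiographic Assessments):** after describing local CT/MRI and bone scans every 6 months, reviewed by the investigator, it says "Study treatment will be stopped upon disease progression as assessed by the investigator".
- **Section 18.3.4 (Monitoring PSA Progression):** "Study drug administration should continue regardless of PSA values until radiographic progression is confirmed by local imaging (CT/MRI"), on the investigator's assessment, "and the investigator considers continuing study drug not to be beneficial".
- **Section 18.5 (Duration of Treatment and Dose Modification):** "Open-label study treatment administration may continue for patients whose prostate cancer has not progressed radiographically".
- **Synopsis, open-label period:** "Patients will not continue in the open-label period if they have had radiographic cancer progression".

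Two further places bear on the question. Section 18.7, when reserving the sponsor's right to terminate the study, promises that "study treatment will be available to all patients who participate in the OL period for as long as they are deriving clinical benefit". It also sends the reader to Section 5.3 for details of permanent discontinuation. The progression entry in the Section 5.3 list is "Development of radiographic progression confirmed by central review after initial local read". Section 18.1 says that central reading ended on 31 March 2023.

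**The concern.** The open-label period is running, so these are live instructions. A site can find textual support for stopping in 18.3.3 and for continuing in 18.3.4, for the same patient on the same day. The main consequences are these.

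- **Exposure and safety window.** Safety collection runs to 30 days after the last dose (Protocol 18.3.2), and the SAP builds its on-treatment period from the last dose (SAP 3.5). A different stopping date changes how much follow-up counts as on treatment.
- **Deviation classification.** SAP 6.7.3 lists, as a category of major deviation, patients who met a stopping criterion but stayed on drug. A site acting on 18.3.4 could be recorded as deviating from 18.3.3, and monitors cannot apply the category consistently without a single rule.
- **Descriptive updates.** The stopping date can shift the start of the next therapy. That start date feeds time to first new antineoplastic therapy and PFS2, both updated at the final OS analysis (Protocol 18.9; SAP 5.1.2).

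**Working it through.** No arithmetic applies: the point depends on no alpha, effect size or event count. The check is a comparison of the texts.

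**Step 1: do the two sections concern the same event?** Section 18.3.3 says disease progression rather than radiographic progression, but its preceding sentences are about scans and the investigator's review of them. Section 18.3.4 says radiographic progression on local imaging, per the investigator. Both therefore turn on investigator-assessed radiographic progression. Call this P. Let N mean that the investigator sees no benefit in continuing.

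**Step 2: where do the rules differ?** Section 18.3.3 stops when P holds. Section 18.3.4 stops when P and N both hold.

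| P | N | 18.3.3 | 18.3.4 | Agree? |
|---|---|---|---|---|
| No | Either | No stop on this ground | No stop on this ground | Yes |
| Yes | Yes | Stop | Stop | Yes |
| Yes | No | Stop | Continue | **No** |

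Only the last row conflicts: progression is present and the investigator still sees benefit.

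**Step 3: does other text settle it?** The synopsis and Section 18.5 are consistent with 18.3.3, although 18.5 is worded as permission rather than as an instruction to stop. The supply promise in 18.7 leans towards benefit as the test. No sentence ranks one section over another or presents treatment beyond progression as an exception to 18.3.3. Following the 18.7 reference to Section 5.3 does not help, because the progression criterion there requires a central read and none has been made since 31 March 2023.

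**Step 4: is the imaging the same?** Section 18.3.3 lists CT/MRI and bone scan. Section 18.3.4 names only CT/MRI in its parenthesis on confirmation. Under Section 9.1.2.1.2, bone lesions in a single region need a second modality (plain film, CT or MRI), whereas lesions in 2 or more of the 5 regions do not. Multi-region progression seen only on bone scan thus meets 18.3.3 but, read literally, never meets the first condition of 18.3.4. This mismatch is separate from the benefit clause.

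**The case against.** The strongest reply is that 18.3.4 is about PSA. The sentence closes a paragraph on restarting treatment, and its evident purpose is to say that a rising PSA alone is no reason to stop. It closely follows Section 9.1.3.1 of the main protocol, with local imaging in place of central. Section 18.3.3 is the section on assessing progression, and the synopsis and 18.5 stand with it, so three places point one way and one trailing clause the other. The 18.7 sentence concerns supply if the sponsor ends the study and is not a stopping rule.

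Much of this is fair, and it explains how the clause arose. But the words of 18.3.4 still set a joint end condition for giving drug, and nothing tells a site to disregard it. On imaging, the reply is that naming CT/MRI as confirmation need not exclude bone scan as detection. That works for single-region lesions, but not for multi-region lesions, which need no second modality.

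Three stronger readings are tempting and should be resisted.

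- **A reader might infer that every patient who progresses is affected.** The table shows otherwise: where the investigator sees no further benefit, both sections lead to stopping, apart from the literal bone-scan gap.
- **A reader might infer that the trial's formal results are at risk.** The final MFS analysis is complete. OS is the only endpoint still to be formally tested, and it is analysed by intention to treat. The other updates are descriptive, and the SAP's on-treatment period follows each patient's actual last dose or start of new therapy under either rule.
- **A reader might extend the point to the double-blind period,** since Sections 5.3 and 9.1.3.1 show the same split. That period has concluded, so the comparison explains the origin of the wording but leaves little to act on.

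**Conclusion.** The point holds as an internal contradiction in live treatment-stopping instructions. It is limited to patients with investigator-assessed radiographic progression whom the investigator still judges to benefit. The CT/MRI parenthesis and the obsolete route to Section 5.3 are secondary defects. The documents give no count of patients in this position, so the size of any effect on exposure, safety follow-up, deviation counts or the descriptive updates cannot be stated. No alpha, power, event count or OS test changes.

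The conclusion rests on two readings: that progression in 18.3.3 means radiographic progression, as its context indicates, and that the conjunction in 18.3.4 is meant literally. If the sponsor intended that clause only as a statement about PSA, the contradiction is one of drafting, but sites still need it corrected. The clarification should be made; nothing in the analysis plan depends on it.

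**What to change.** State one open-label stopping rule at radiographic progression, in one place, with one list of imaging modalities that says explicitly how progression seen only on bone scan is handled. Have the synopsis and Sections 18.3.3, 18.3.4 and 18.5 refer to it. In Section 18.7, amend the reference to Section 5.3 so that it no longer leads to a criterion needing central review. If the PSA sentence in 18.3.4 is kept, make clear whether the benefit clause is part of the rule. Identify the same rule as the criterion for the SAP 6.7.3 deviation category in the open-label period.

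Which rule applies is a clinical decision for the sponsor and investigators, and this review takes no position on it. The cost is a protocol clarification; no additional data or analyses are needed.
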